16.1 Study Design/Endpoints

This multicenter, Phase II open label study will determine the safety and tolerability of patients with stage III/IV HIV- associated Hodgkin Lymphoma and evaluate the treatment effect of AVD in addition to brentuximab vedotin (SGN- 35). The primary objective of the Phase II portion of the study is to establish an estimate of the two-year progression-free survival for patients using brentuximab vedotin plus AVD regimen with HIV-associated advanced stage Hodgkin lymphoma.

The primary endpoint will estimate the two-year progression-free survival for AVDbrentuximab vedotin which will be done using a one sample nonparametric survival analysis.

Secondary objectives include:

- 1. To evaluate toxicity of AVD and brentuximab vedotin with HAART.
- 2. To estimate the partial response (PR) rate, complete response (CR) rate, overall survival (OS), event free survival at 2 and 5 years.
- 3. To evaluate effect of AVD and brentuximab vedotin on CD4 and CD8 counts after cycle 1, 4, at the end of therapy, and every 3 months after treatment completion for one year.
- 4. To investigate the prognostic value of FDG-PET/CT scans at baseline, after cycle 2, and at treatment completion, with respect to 2 year progression free survival.
- 5. To evaluate HAART status at baseline and to correlate this with tumor response to therapy and OS and PFS.
- 6. To characterize the histologic subtypes in HIV-HL in the highly active antiretroviral therapy (HAART) era.
- 7. To assess the neurotoxicity of HAART in combination with AVD and brentuximab vedotin.
- 8. To evaluate effect of AVD and brentuximab vedotin on viral load after cycles 1, 4, at completion of therapy, and every 3 months after treatment completion for one year.
- 9. To perform pharmacokinetic and immunogenicity studies to determine drug levels during therapy (not applicable for French participants).
- 10. To perform miRNA profile analysis on the HIV-HL tumor specimens and to correlate miRNA expression with OS, PFS, tumor response to therapy, histologic subtype of HIV-HL, and HIV disease characteristics not applicable for French participants).
- 11. To perform tissue microarray analysis on HIV-HL tumor specimens and to correlate the markers studied with OS, PFS, and tumor response to therapy (not applicable for French participants).
- 12. To identify EBV associated tumor derived DNA in the plasma of study patients, and to correlate these levels during therapy with disease response and OS (not applicable for French participants).
- 13. To identify cytokines in the plasma of patients during therapy, that can be used as tumor and prognostic markers. (Not applicable for French participants).
- 14. To assess latent and expressed HIV reservoirs before, during, and post chemotherapy. To understand how cytotoxic chemotherapeutic agents effect HIV expression (not applicable for French participants).

16.2 Sample Size/Accrual Rate

In the Phase II portion of the study, 51 patients will be enrolled worldwide to estimate the 2-year progression free survival. Sample size calculation is based on providing an estimate of the PFS with a 95% confidence interval $\pm 10\%$ under the hypothesis that 2-year PFS is 85%.

The primary endpoint of the phase II portion will be to estimate the two-year progression-free survival for AVD- brentuximab vedotin which will be done using Kaplan-Meier estimates and corresponding 95% confidence intervals based on standard errors using Greenwood's formula.

16.3 Stratification Factors

No stratification is planned for this study.

16.4 Analysis of Secondary Endpoints

Descriptive summaries and exploratory analyses for secondary objectives will be conducted. Significance for comparisons will be at the p<0.05 level.

Secondary objectives include:

- 1. To evaluate toxicity of AVD and brentuximab vedotin with HAART.
- 2. To estimate the partial response rate, complete response rate, overall survival (OS), event free survival at 2 and 5 years.
- 3. To evaluate effect of AVD and brentuximab vedotin on CD4 and CD8 counts after 2 cycles, 6 cycles, and every 3 months after treatment completion for one year.
- 4. To evaluate effect of AVD and brentuximab vedotin on viral load after 2 cycles, 6 cycles, and every 3 months after treatment completion for one year.
- 5. To investigate the prognostic value of FDG-PET scans at baseline and after 2 cycles in patient with HIV and HL with respect to 2 year progression free survival.
- 6. To evaluate HAART status at baseline for difference in outcome.
- 7. The characterization of histologic subtypes in HIV-HL in the HAART era.
- 8. To assess additional neurotoxicity in combination with HAART and AVD and brentuximab vedotin.

The frequency of AEs and their severity will be tabulated to evaluate tolerance of AVD and brentuximab vedotin with HAART. Further, binomial probabilities and their 95% confidence intervals will be used to estimate the response rates (i.e., partial response rate, complete response rate, overall response rate) and event free survival at 2 and 5 years of AVD and brentuximab vedotin for a treatment of patients with stage III/IV HIV-associated Hodgkin Lymphoma.

Repeated measures analysis of variance (ANOVA) models will be used to evaluate the effect of AVD and brentuximab vedotin on CD4 counts, CD8 counts and viral load after 1, 4, and 6 cycles, and every 3 months after treatment completion for one year.

Log-rank analysis will be used to investigate the prognostic value of FDG-PET scans at baseline, after 2 cycles and post-therapy in patients with HIV and HL with respect to progression free survival.

After cycle 2 and post-therapy, progression-free survival will be estimated for patients whose FDG-PET findings were negative and those whose findings were positive using Kaplan-Meier estimates and corresponding 95% confidence intervals based on standard errors using Greenwood's formula. Positive predictive value after 2 cycles and post-therapy will be estimated as the proportion of PET-positive patients who progress or

die before two years; negative predictive value after 2 cycles and post-therapy will be estimated as the proportion of PET-negative patients who are progression-free and alive at two years. Sensitivity of FDG-PET at cycle 2 and post-therapy will be estimated as the proportion of patients who progressed or died prior to year 2 whose FDG-PET was positive. Specificity of FDG-PET at cycle 2 and post-therapy will be estimated as the proportion of patients who are alive and progress-free at 2 years whose FDG-PET was positive. Exact two-sided 95% confidence intervals will be used for all estimates.

Log-rank analysis will be used to evaluate HAART status at baseline for difference in outcome in terms of overall survival and progression free survival. The frequency and proportion of different histologic subtypes will be calculated.

The frequency of neurotoxicity in patients taking AVD and brentuximab vedotin in combination with/without HAART will be tabulated. A binomial test of proportions will be used to test the difference in additional toxicity between those patients taking AVD and brentuximab vedotin on HAART vs. those patients not on HAART.

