After cycle 2 and post-therapy, progression-free survival will be estimated for participants whose FDG-PET findings were negative and those whose findings were positive using Kaplan-Meier estimates and corresponding 95% confidence intervals based on standard errors using Greenwood's formula. Positive predictive value after 2 cycles and post-therapy will be estimated as the proportion of PET-positive participants who progress or die before two years; negative predictive value after 2 cycles and post-therapy will be estimated as the proportion of PET-negative participants who are progression-free and alive at two years. Sensitivity of FDG-PET at cycle 2 and post-therapy will be estimated as the proportion of participants who progressed or died prior to year 2 whose FDG-PET was positive. Specificity of FDG-PET at cycle 2 and post-therapy will be estimated as the proportion of participants who are alive and progress-free at 2 years whose FDG-PET was positive. Exact two-sided 95% confidence intervals will be used for all estimates.

Log-rank analysis will be used to evaluate HAART status at baseline for difference in outcome in terms of overall survival and progression free survival. The frequency and proportion of different histologic subtypes will be calculated.

The frequency of neurotoxicity in participants taking AVD and brentuximab vedotin in combination with/without HAART will be tabulated. A binomial test of proportions will be used to test the difference in additional toxicity between those participants taking AVD

and brentuximab vedotin on HAART vs. those participants not on HAART.

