9.5 Follow-up assessments

The studies listed below will be repeated post-therapy within 6-8 weeks of the last treatment dose (6-8 weeks after Cycle 6 Day 15) and then every 3 months (+/- 7 days) thereafter for 2 years; every 6 months (+/- 7 days) for the third through the fifth years unless otherwise specified. All study subjects should be followed for up to 5 years after treatment discontinuation or until death if occurring before 5 years of treatment discontinuation. Patients who discontinue all protocol therapy after a CR or PR are followed for up to 5 years after treatment for recurrence and survival. Patients who discontinue protocol therapy due to disease progression or other reasons are followed for survival for up to 5 years after treatment discontinuation. No additional studies except follow up for survival are required after disease progression. In those instances in which a third party payer denies payment for some or all of these laboratory analyses, absence of these test results will not be considered a protocol violation.

- 1. Medical history.
- 2. Physical examination, including performance status (see Appendix 20.5,

Performance Status Scale), vital signs (weight, height, body surface area), neurological examination, and if possible, two dimensional measurement of all palpable, peripheral lymph nodes and measurement of other sites of disease present on physical exam.

- 3. At the conclusion of chemotherapy, a full body FDG-PET/CT scan will be done between 6-8 weeks post the final treatment dose, Cycle 6 Day 15. This will be the final FDG-PET/CT needed for the study. A combined FDG-PET/CT or FDG-PET + CT scans with and without IV contrast are required for the post- treatment scan. If a patient has an allergy to IV contrast, a CT scan without contrast will be permitted. As the false positive rate of FDG-PET scans may be higher in the HIV population, a biopsy of an unexpected FDG-PET avid lesion is recommended but remains at the discretion of the investigator.
- 4. **CT scan** with oral/IV contrast every 6 months for 5 years. To begin 6 months from the post treatment FDG- PET/CT scan, obtained 6-8 weeks post the final chemotherapy dose (See Section 9.5).
- 5. **PFT** with volumes, spirometry, DLCO and pulse oximetry for any patient with a DLCO corrected for hemoglobin \leq 70% during therapy. To be repeated at all post-treatment evaluations until normalization.

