9.6 Early Discontinuation of Therapy

Subjects discontinuing therapy early (i.e., PD or stable disease, administrative reasons, subject non- compliance, etc.) will have a medical history update and complete physical examination. The examination will include performance status and blood drawn for the following studies within 1 month after treatment discontinuation, unless otherwise noted. See Section 12 for a list of reasons for study termination. Subjects will be followed for survival only for 5 years after the last date of treatment:

- **CBC** with differential.
- Serum chemistries: electrolytes (Na, K, Cl, bicarbonate, Ca, Mg, and phosphorus), glucose, blood urea nitrogen (BUN), creatinine, total bilirubin, alkaline phosphatase (ALP), LDH, total protein, albumin, AST and ALT.
- **CD4 and CD8 cell** count (do not repeat if done within 1 month from removal from treatment).
- **HIV-1 RNA viral load** to be evaluated at the local laboratory, do not repeat if done within 1 month from removal from treatment).

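### PET predictive values at two years are crude proportions with no rule for patients whose progression follow-up ends early, beside Kaplan-Meier estimates for the same groups

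*Combined protocol and SAP*

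**What the plan says.** French protocol 16.4 and AMC protocol 11.4 give the same plan, and French section 16.0 says that the data will be pooled for analysis.

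- For the interim and end-of-treatment scans, the plan states: "progression-free survival will be estimated for patients whose FDG-PET findings were negative and those whose findings were positive using Kaplan-Meier estimates", with Greenwood standard errors.
- NPV is "estimated as the proportion of PET-negative patients who are progression-free and alive at two years"; the AMC text reads "estimated as the proportion of PET-negative participants who are progression-free and alive at two years".
- The PPV sentence begins "Positive predictive value after 2 cycles and post-therapy will be estimated as the proportion of PET-positive patients who progress or" and finishes with death before two years.
- Sensitivity is taken among patients who had an event before year 2, and specificity among patients alive and progression-free at two years.
- "Exact two-sided 95% confidence intervals will be used for all estimates".

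No sentence covers unknown two-year progression status. The follow-up sections show where it can arise. French 9.5 says "Patients who discontinue protocol therapy due to disease progression or other reasons are followed for survival for up to 5 years after treatment discontinuation". French 9.6, on early discontinuation, says "Subjects will be followed for survival only for 5 years after the last date of treatment". AMC 8.3 and 8.4 match. French 13.2 and 13.3 foresee consent withdrawal and loss to follow-up.

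**The concern.** Two-year progression-free survival in PET-negative patients is the NPV, and one minus that survival in PET-positive patients is the PPV. The plan therefore estimates each quantity twice, once by a method that handles censoring and once by a method that does not. Exact binomial intervals assume that every patient's status is known.

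The patients at issue stop being assessed for progression before two years and are not known to have progressed or died. They may have stopped treatment early and moved to survival-only follow-up, withdrawn consent or been lost. If they remain in the NPV denominator, loss of follow-up looks like failure of the scan.

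The prognostic value of PET is a named secondary objective. AMC 4.6.8 and French 13.1 say that PET is not yet validated in this disease, and AMC 2.6 calls validating the cycle 2 scan an important goal. An NPV lowered by follow-up loss would bear directly on that goal.

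**Working it through.** **The plan's own figure.** The documents give no PET-group sizes, predictive values or dropout rate. The only related figure is the sample size: 51 for a 95% interval of ±10 points at a two-year PFS of 85%. The formula gives n = (1.96/0.10)² × 0.85 × 0.15 = 48.98, so 49. At 51 the half-width is 9.8 points. The 51 is consistent with its stated basis.

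**Assumed inputs.** 41 PET-negative patients with true two-year PFS of 90% and 10 PET-positive with 65%. Overall this is (41 × 0.90 + 10 × 0.65)/51 = 43.4/51 = 85.1%, close to the planning value. Progression follow-up is lost by two years in a fraction L = 5%, 10% or 15%, independently of outcome, with exponential times.

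**Formulas.**
- NPV, literal denominator: 0.90 × (1 − L).
- Coverage of 90% by the exact interval: the event-free count is binomial with n = 41 and probability 0.90 × (1 − L); sum over counts whose interval contains 0.90.
- PPV, literal denominator: [h/(h + c)] × [1 − 0.65(1 − L)], where h = −ln(0.65)/2 and c = −ln(1 − L)/2. At L = 10%: h = 0.2154, c = 0.0527, giving 0.8035 × 0.415 = 33.3%.
- Known-status versions: the same counts, with unknowns removed from the denominator.

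| L | NPV literal | Exact-interval coverage | NPV known-status | PPV literal | PPV known-status |
|---|---|---|---|---|---|
| 0% | 90.0% | 96.9% | 90.0% | 35.0% | 35.0% |
| 5% | 85.5% | 86.8% | 89.8% | 34.2% | 35.6% |
| 10% | 81.0% | 62.5% | 89.5% | 33.3% | 36.3% |
| 15% | 76.5% | 34.8% | 89.2% | 32.5% | 37.0% |

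At 10% loss the two readings of the NPV sentence differ by 89.5 − 81.0 = 8.5 points.

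**Same data, two estimators.** Take 40 PET-negative patients with events at months 5, 9, 14 and 20.
- Nobody censored: 36/40 = 90.0% by both methods.
- Four patients last assessed at month 3: crude 32/40 = 80.0% (exact 64.4% to 90.9%); Kaplan-Meier 32/36 = 88.9%.
- The same four last assessed at month 12: crude 80.0%; Kaplan-Meier (38/40) × (32/34) = 89.4%.
- Eight censored: crude 28/40 = 70.0%; Kaplan-Meier 87.5% (month 3) or 88.7% (month 12).

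For PPV, take 8 PET-positive patients with 3 events and 2 censored before the first event. The crude value is 3/8 = 37.5%; one minus Kaplan-Meier is 3/6 = 50.0%.

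**Does the replacement perform?** Simulation under the assumed inputs, 6,000 runs per setting, L from 0 to 15%:
- The Kaplan-Meier mean is within about 0.2 points of the truth in both groups.
- Plain Greenwood intervals cover 89% to 92% (n = 41) and 87% to 89% (n = 10), below nominal.
- Log-log intervals cover 94% to 96%. An exact interval replaced them in the 1% to 2% of runs without events, where log-log is undefined.

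**The case against.** The strongest reply is that neither protocol says all PET-negative patients, or that unknowns count as failures. Sensitivity and specificity in the same paragraph are conditioned on known outcomes, and a patient of unknown status has no cell in a two-by-two table. Dropping unknowns is therefore at least as natural a reading, and it keeps the NPV within about one point. This stands: a reader might infer that the plan deliberately scores lost patients as failures, but the text does not say so. What remains is that neither rule is written, and dropping unknowns pushes PPV up by 0.6 to 2.0 points on the assumed inputs.

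Second, the affected group is narrower than French 9.6 suggests. AMC 4.5 and 8.3 and French 9.5 keep patients who stop after a complete or partial response in follow-up for recurrence, and PET-negative patients are plausibly mostly responders. Early discontinuers have no scheduled post-therapy PET, so the survival-only route hardly touches the post-therapy measures. This also stands, although AMC 8.4 and French 9.6 state no exception for responders. Other early stops, withdrawals and losses remain.

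Third, with five years of planned follow-up, censoring before two years need not be common, and the loss rates here are assumed. Correct: with no such censoring the two methods agree exactly.

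Fourth, plain Greenwood intervals under-cover at these group sizes, while known-status proportions with exact intervals cover 96% to 98%. This is right and changes the remedy. Kaplan-Meier also assumes non-informative censoring, which stopping for toxicity or stable disease may violate.

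**Conclusion.** The gap is real and worth closing, within limits. NPV and PPV have no rule for unknown two-year status, although both protocols allow such patients to arise. On the literal reading, NPV is biased down by roughly the fraction lost: 4.5 to 13.5 points for 5% to 15% loss, with 41 PET-negative patients and a true 90%. PPV is biased down by 0.8 to 2.5 points. On the known-status reading, NPV is off by 0.8 points or less.

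Two stronger conclusions are not supported. A reader might infer that the report must show contradictory figures; it will do so only if someone is censored before two years, and the documents give no rate. A reader might also extend the defect to sensitivity and specificity; their wording already conditions on known outcomes, so they need a stated rule but do not count lost patients as failures.

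These are exploratory secondary analyses and the primary endpoint is unaffected. The censoring-adjusted curves are already planned beside them, so this is a change that should be made rather than one on which the trial depends.

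**What to change.** In French 16.4 and AMC 11.4:

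1. Define NPV as the two-year Kaplan-Meier PFS in PET-negative patients, and PPV as one minus the two-year Kaplan-Meier PFS in PET-positive patients.
2. Use log-log intervals instead of plain Greenwood, because the groups are small and estimates may lie near 100%. Name an exact interval for a group without events.
3. Report the known-status proportions with exact intervals as a sensitivity analysis, with the number of unknowns in each PET group.
4. State that sensitivity and specificity either use patients with known two-year status or are derived from the Kaplan-Meier values and the PET-positive fraction π. In the second case, sensitivity = π·PPV / [π·PPV + (1 − π)(1 − NPV)] and specificity = (1 − π)·NPV / [(1 − π)·NPV + π(1 − PPV)], with bootstrap intervals. The specificity sentence in both protocols refers to a positive scan and needs correcting in the same edit.
5. State the start of the two-year clock for these measures; neither protocol does.

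The cost is wording and a few lines of code, with no new data. The main intervals would no longer be exact, and the estimates would rest on non-informative censoring, which the sensitivity analysis does not remove.

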17.0 STUDY MONITORING

17.1 Responsibilities of investigators

The investigator(s) undertake(s) to perform the study in accordance with Good Clinical Practice and specifically either European 2001/20/CE and 2005/28/CE directives, ICH E6 or US regulations 21 CFR - Part 312 subpart D and guidelines for the monitoring of clinical investigations.

The investigators ensure compliance with respect to the investigational drug schedule, visit schedule and procedures required by the study. The investigators agree to provide all information requested in the case report form in an accurate and legible manner according to instructions provided.

As may be required by the local legislation, the investigators will check that the patients are directly or indirectly affiliated to the national health insurance or coverage system if there is any.

17.2 Responsibilities of the sponsor

The sponsor (LYSARC) of this study in France has responsibilities to health authorities to take all reasonable steps to ensure the proper conduct of the study as regards ethics, study adherence, integrity and validity of the data recorded on the case report forms. Thus, the main duty of the sponsor project leader and of the Sponsor clinical research support team (LYSARC) is to help the investigator maintaining a high level of ethical, scientific, technical and regulatory quality in all aspects of the study.

At regular intervals during the study, the center will be contacted, through site visits, letters or telephone calls, by a representative of the project team (LYSARC) to review study progress, investigator and subject adherence to study requirements and any emergent problems.

During monitoring visits, the following points will be assessed with the investigator or a designee for each patient selected and included: subject informed consent signature, patient eligibility (inclusion and exclusion criteria), subject recruitment and follow-up, subject compliance to the study treatment, study treatment accountability (if applicable), concomitant therapy use, evaluations of response, serious/non serious adverse event documentation and reporting, and quality of data. Sections of Case Report Forms may be collected/entered (in case of e-CRF) on a visit per visit basis. A monitoring plan will be written describing monitoring process.

